5 STUDY POPULATION

Approximately 510 subjects (170 in each treatment group) are planned to be randomized.

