7.4. Planned Study Analyses

7.4.1. Statistical Summaries: Descriptive and Inferential

All statistical tests will be two-sided and a difference resulting in a p-value of less than or equal to 0.05 will be considered statistically significant. All p-values will be rounded to and displayed in four decimals. If a p-value less than 0.0001 occurs it will be shown in tables as <0.0001.

Descriptive summaries of variables will be provided where appropriate. For continuous variables, the number of non-missing values (n) and the median, mean, standard deviation, minimum, and maximum will be tabulated by treatment. For categorical variables, the counts and proportions of each value will be tabulated by treatment. Expansion of descriptive table categories within each treatment may occur if such elaborations are thought to be useful.

For the summary statistics of all numerical variables unless otherwise specified, minimum and maximum will be displayed to the same level of precision as reported. Mean and median will be displayed to one level of precision greater than the data collected. The standard deviation / standard error will be displayed to two levels of precision greater than the data collected.

Change from baseline scores will be calculated as the post-baseline measurement minus the baseline value.

All collected data will be presented in listings. Data not subject to analysis according to this plan will not appear in any tables or figures but will be included in the data listings.

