9.1.2. Co-Primary Efficacy Analyses

The AERT 40 mg dose will be compared with placebo first (for both TNmAS-MAL and CGIC). If both comparisons are significant at the 0.05 level then the AERT 80 mg dose will be tested at the 0.05 level (both TNmAS-MAL and CGIC). Both co-primary efficacy endpoints need to meet the 0.05 level for the AERT 40 mg dose comparison with placebo for the study to be considered a success. Therefore, no adjustment for multiplicity is needed. The Day 84 comparison is the primary time point for both co-primary endpoints.

Descriptive statistics for each co-primary efficacy variable will be tabulated by study visit and treatment group. CGIC categories will also be summarized by frequencies and percentages by study visit and treatment group.

Note that if two or more limbs tie for Most Affected at baseline, then the Visit 5 (Day 84) scores for the tied limbs are assessed and the one with the worst score at Visit 5 becomes the Most Affected Limb in the primary analysis. In the case of a tie at baseline and at Visit 5, then both scores from Visit 4 and Visit 5 are summed for each limb and the highest (worst) total is flagged as the Most Affected Limb.

TNmAS-MAL will be analyzed using a restricted maximum likelihood (REML)-based mixed model for repeated measures (MMRM) with fixed effects for treatment, visit, study center, and the treatment-by-visit interaction; and with baseline score as a covariate. The outcome variable will be change from baseline scores. Study visit will be included in the model as a categorical variable (Visit 4 [Day 42] and Visit 5 [Day 84]) along with the treatment-by-visit interaction. Least squares means (LS means) will be used to compare treatments.

CGIC will also be analyzed using an REML-based MMRM with fixed effects for treatment, visit, study center, and the treatment-by-visit interaction. As the CGIC is a change score, no value is measured at baseline. The outcome variable will be CGIC scores. Study visit will be included in the model as a categorical variable (Visit 4 [Day 42] and Visit 5 [Day 84]) along with the treatment-by-visit interaction. LS means will be used to compare treatments.

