For both models, pairwise treatment comparisons between the two AERT doses and placebo will be performed at each visit; however, the primary comparisons will be the contrasts between AERT 40 mg and placebo at Day 84. Unstructured covariance matrices will be utilized. If the model fails to converge with an unstructured covariance matrix other structures will be tried and the structure with the lowest corrected Akaike information criterion (AICC) will be used for the analysis. Full details will be included in the CSR. The Kenward Roger method will be used for computing the denominator degrees of freedom for the tests of fixed effects. Study centers may be pooled prior to unblinding.

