median. For any subject that discontinues for any reason, check to see if his or her TNmAS-MAL change from baseline score for the current visit is less than the median for the current visit described above (do this for every visit for which the subject has a score available). If the early termination visit falls between two scheduled visits, the medians calculated from the scheduled visits will be interpolated to the termination time. If the subject's score is less than the median at that visit, then scale the subject's current score by multiplying it by the subject's last week that the TNmAS-MAL score is observed divided by 12. For example, if a subject discontinues and has the final TNmAS-MAL score at Week 7, then anytime the subject has a score less than the respective within treatment/visit median described above, that score will be multiplied by 7/12. These new scores are then used in the primary efficacy MMRM model.

A similar approach will be used for CGIC. CGIC values of 1 (very much improved), 2 (much improved), or 3 (improved) will be utilized to determine the median.

- The impact of missing data will be determined in an analysis using an analysis of covariance (ANCOVA) model based on multiple worst observation carried forward (mWOCF) imputed data. For mWOCF imputed data, subjects who withdraw from the trial early due to an AE will have their missing data imputed using WOCF; all other missing data will be imputed using the last observation carried forward (LOCF). The models will include treatment and study site as fixed effects. The model for TNmAS will also include baseline score as a covariate.
- The primary efficacy analysis model (MMRM) makes the assumption that missing data are “missing at random” (MAR). When data are MAR, the missingness of the data does not depend on the missing value after conditioning on the observed data (i.e., prior assessments and baseline covariates). Note that when the missingness of the data depends on the values of the missing variables after conditioning on the observed data, the data are called “missing not at random” (MNAR). In order to assess the MAR assumption, a placebo-based pattern mixture model (PMM) will be utilized following the steps outlined in Ratitch B and O’Kelly, M.J. (2011) for both TNmAS-MAL and CGIC.

[figure not shown]
Briefly, the strategy for implementing this approach is as follows for subjects with missing data:

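### The TNmAS-MAL MMRM holds one baseline slope for Day 42 and Day 84; if the true slope changes and baseline-related dropout differs by arm, the Day 84 contrast can be biased even under MAR

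*SAP*

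**What the plan says.** SAP 9.1.2 models TNmAS-MAL by REML with "fixed effects for treatment, visit, study center, and the treatment-by-visit interaction; and with baseline score as a covariate". Protocol 11.4.1 specifies the same terms. On the outcome the SAP states: "The outcome variable will be change from baseline scores". Two post-baseline visits enter as categories, Day 42 and Day 84. On the covariance: "Unstructured covariance matrices will be utilized". The SAP also states that "the primary comparisons will be the contrasts between AERT 40 mg and placebo at Day 84".

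SAP 9.1.3 says the primary model assumes MAR, meaning that "the missingness of the data does not depend on the missing value after conditioning on the observed data", where the observed data include earlier assessments and baseline covariates.

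No sensitivity analysis of the co-primary endpoints lets the baseline slope vary by visit. SAP 9.2.2 allows extra interaction terms, but only for secondary endpoints.

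**The concern.** MAR protects a likelihood-based analysis only if the mean model is right. Here every part of the model is free to differ by visit except the baseline slope and the center effects. If the Day 84 slope differs from the Day 42 slope, the fitted common slope is a compromise, and the Day 84 mean that the model implies for subjects missing at Day 84 is wrong. If the missing subjects have a different baseline profile in the two arms, that error does not cancel in the contrast.

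Both conditions are plausible, though neither is documented:

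- **Slope.** For a change score the baseline slope is ρ × (SD at visit / SD at baseline) − 1. With equal SDs, a correlation with baseline that falls from 0.7 to 0.6 gives slopes of −0.3 and −0.4. The tie rule for the most affected limb also uses the Day 84 score, so it could shift the Day 84 slope if ties vary with baseline level.
- **Dropout.** Anti-spasticity drugs are withdrawn before baseline, and starting another is a ground for withdrawal (Protocol 12.4), which could remove more spastic placebo subjects. On AERT, withdrawal may be driven more by tolerability. SAP 9.1.3 foresees that discontinuation may differ by dose.

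At stake is the TNmAS-MAL half of the comparison that decides study success and opens testing of 80 mg (SAP 7.5).

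**Working it through.** **Inputs from the documents.** "Approximately 510 subjects (170 in each treatment group) are planned to be randomized" (Protocol 5): 3 × 170 = 510, which agrees. Two visits; unstructured covariance; two-sided 0.05. The public copy shows no text under the sample-size headings, so effect size, SD, dropout and slopes are assumptions below.

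**Cost of the term.** Fixed-effect columns without center: intercept 1 + treatment 2 + visit 1 + treatment-by-visit 2 + baseline 1 = 7. Baseline-by-visit adds 2 − 1 = 1, giving 8.

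**Why two conditions are needed.** Take the simple case where everyone has Day 42 data. Let β42 and β84 be the true slopes, b the fitted common slope and φ the regression of Day 84 on Day 42. Then

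bias ≈ [(β84 − b) − φ(β42 − b)] × (mean baseline of those observed at Day 84 on 40 mg − same on placebo).

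The first factor is zero when the slopes are equal. The second is zero in expectation when dropout selects on baseline alike in both arms, or not at all.

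**Simulation.** The planned three-arm, two-visit model (center omitted) was fitted with and without baseline-by-visit: 3,000 trials of 170 per arm per row. Assumed: baseline SD 3, residual SD 3, correlation 0.6, slope −0.3 at Day 42 and −0.3 − d at Day 84, true difference 0. Dropout depended on baseline only (so MAR), and half of dropouts also missed Day 42. Rates and logit slopes per baseline SD are in the order placebo/40 mg/80 mg. Negative bias favours AERT.

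| Dropout | Logit slopes | d | Bias, planned | Bias, with term | SE, planned / with term | Type I, planned / with term |
|---|---|---|---|---|---|---|
| none | – | 0.2 | +0.003 | +0.004 | 0.327 / 0.325 | 0.049 / 0.048 |
| 20/20/20% | 0.7/0.7/0.7 | 0.2 | −0.002 | −0.002 | 0.359 / 0.357 | 0.052 / 0.051 |
| 10/20/30% | 0/0.7/0.7 | 0 | +0.006 | +0.006 | 0.349 / 0.349 | 0.050 / 0.049 |
| 10/20/30% | 0.7/0.7/0.7 | 0.2 | +0.029 | +0.001 | 0.351 / 0.349 | 0.050 / 0.050 |
| 10/20/30% | 0/0.7/0.7 | 0.2 | +0.045 | −0.011 | 0.351 / 0.349 | 0.050 / 0.052 |
| 10/20/30% | 0/0.7/0.7 | 0.3 | +0.083 | +0.001 | 0.354 / 0.349 | 0.056 / 0.053 |
| 20/20/20% | 0.7/−0.7/−0.7 | 0.2 | −0.109 | +0.002 | 0.360 / 0.359 | 0.064 / 0.053 |
| 30/30/30% (extreme) | 1/−1/−1 | 0.3 | −0.353 | −0.012 | 0.387 / 0.384 | 0.151 / 0.048 |

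Monte Carlo error is about 0.35/√3000 = 0.006 for bias and √(0.05 × 0.95/3000) = 0.004 for type I error. In SE units: 0.029/0.351 = 0.08; 0.083/0.354 = 0.23; 0.109/0.360 = 0.30; 0.353/0.387 = 0.91.

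With 10/20/30% dropout unrelated to baseline (100,000 per arm), adding the term moved the contrast by at most 0.002 at any d.

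**A second pattern.** With the same SDs and correlation, 40,000 per arm, placebo dropout of 15–20% rising with baseline and 40 mg dropout of 20–22% unrelated or weakly inverse, the planned model's bias was −0.02 to −0.04 for d = 0.1, −0.05 to −0.08 for d = 0.2 and −0.07 to −0.11 for d = 0.3. With the term it stayed within about 0.005 of zero.

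**The case against.** The strongest reply is that this is good practice rather than a demonstrated defect. Much of it stands.

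- A reader might infer that baseline-related dropout alone biases the contrast. It does not: the second and third rows of the table show none when dropout is alike across arms or when the slopes are equal. The documents report neither changing slopes nor dropout linked to baseline. SAP 9.1.3 raises differential discontinuation only as a possibility, chiefly at 80 mg, and does not mention baseline.
- A reader might infer that the error favours AERT. The sign is not fixed: the 10/20/30% rows with d above 0 run against AERT, the opposite-dropout rows in its favour.
- A reader might infer a real loss of precision. The largest SE gap in the table is 0.354 against 0.349, about 1%.
- Protocol 6.5 and 12.4 ask for TNmAS-MAL at early termination, and SAP 7.3.3 assigns it to the closest or next available visit. A subject leaving after Visit 4 can therefore supply a Day 84 value, so true missingness may be below the assumed rates. Many who leave before Day 42 would still lack one.
- The mWOCF ANCOVA, if fitted at Day 84, has its own slope, but on carried-forward data.
- In the placebo-based pattern-mixture analysis the MMRM is fitted after all values are imputed, so this route to bias has gone from that step.
- CGIC must also be significant for study success, so this cannot by itself produce a false success.

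What does not fall is the core: the slope restriction is in the model, MAR does not cover it, and no planned co-primary analysis relaxes it.

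**Conclusion.** The point holds as a conditional one and a cheap improvement. A slope that changes between visits, together with baseline-related dropout that differs between 40 mg and placebo, can bias the Day 84 TNmAS-MAL contrast under the plan's own missing-data assumption. Under moderate assumptions the size is about 0.02 to 0.11 points, up to about 0.3 SE, with type I error about 0.050 to 0.064. It became material (0.35 points, type I error 0.151) only with 30% dropout running in opposite directions by arm. All of these sizes rest on assumed SDs, correlation, slopes and dropout. The existence of the restriction, and the single degree of freedom needed to lift it, do not.

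**What to change.** Before unblinding, add the baseline TNmAS-MAL-by-visit interaction to the TNmAS-MAL MMRM in SAP 9.1.2 and Protocol 11.4.1. Carry it to the MMRM repeats (mITT, per-protocol, early-withdrawal penalty and two-arm analyses) and, with its own baseline, to TNmAS-TL. Use it in the analysis step of the pattern-mixture model only for consistency. Leave CGIC as it is.

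The cost is one term in the text and code, one degree of freedom, and at most about 1% in variance if the slopes are truly equal. In the simulations the SE was unchanged or slightly smaller with the term. It should be prespecified, since adding it after unblinding would look like a choice made on the result.

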8.2 Clinical Global Impression of Change

The CGIC was developed for use in National Institute of Mental Health (NIMH)-sponsored clinical trials to provide a brief, stand-alone assessment of the clinician's view of the subject's global functioning prior to and after initiating a study medication (Guy 1976). The CGIC scale will be used to measure the overall change in the subject's condition since starting the study.

In clinical research, the CGIC is administered by an experienced clinician who is familiar with the disease under study and the likely progression of treatment. Consequently, the CGIC rater can make an expert clinical global judgment about the severity of the illness across various time points within the context of that clinical experience. The clinician makes a judgment about the total picture of the subject at each visit: the illness severity, the subject's level of distress and other aspects of impairment, and the impact of the illness on functioning. The CGIC is rated without regard to the clinician's belief that any clinical changes are or are not due to medication and without consideration of the etiology of the symptoms.

The investigator will evaluate the subject's status on a -3 to +3 scale judging whether there had been a change from significant worsening to significant improvement relative to Visit 2 (Baseline) and must have access to the TNmAS. The CGIC scale is provided in Appendix 3.

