7.2. Covariates and Subgroups

7.2.1. Planned Covariates

The efficacy analyses will include study center as an effect and baseline values (where applicable) as a covariate. Other covariates may be used for exploratory analyses.

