9.2.2. Secondary Efficacy Analyses

Secondary efficacy endpoints will be summarized descriptively and analyzed using the same type of MMRM analysis used for the co-primary efficacy endpoints. PGIC will follow the same MMRM that is used for CGIC. EDSS and TNmAS-TL will follow the same MMRM that is used for TNmAS-MAL. Pairwise comparisons between the AERT doses and placebo will be provided at each visit where data are collected. Additional factors (e.g., baseline renal function) along with interaction terms may be included in the models as sensitivity analyses.

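### The CGIC co-primary model adjusts for no baseline severity measure, although Visit 2 TNmAS-MAL is available; this is a missed precision gain of unknown size, not an error

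*SAP*

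**What the plan says.** SAP 9.1.2 states: "CGIC will also be analyzed using an REML-based MMRM with fixed effects for treatment, visit, study center, and the treatment-by-visit interaction". On the lack of a baseline term it adds: "As the CGIC is a change score, no value is measured at baseline". Protocol 11.4.1 specifies the same model. In the same SAP section the TNmAS-MAL model is fitted to change scores "and with baseline score as a covariate".

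The general rule in SAP 7.2.1 is: "The efficacy analyses will include study center as an effect and baseline values (where applicable) as a covariate". It continues: "Other covariates may be used for exploratory analyses". None of the CGIC sensitivity analyses described in SAP 9.1.3 names a baseline covariate, and the mWOCF ANCOVA gives one to TNmAS only. The imputation code for the pattern-mixture analysis is not in the public copy, so its variable list cannot be seen.

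For the secondary endpoint, SAP 9.2.2 says: "PGIC will follow the same MMRM that is used for CGIC". It also allows: "Additional factors (e.g., baseline renal function) along with interaction terms may be included in the models as sensitivity analyses".

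Both TNmAS-MAL and EDSS are on the Visit 2 schedule (Protocol Table 1). Protocol Section 6 places the TNmAS-MAL ahead of the other visit procedures.

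**The concern.** The absence of a baseline CGIC explains why CGIC cannot be its own covariate. It does not explain why no other baseline severity measure is used, when one is collected on every subject and already serves the companion co-primary model.

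A prognostic link is plausible. Entry requires a TNmAS-MAL of at least 2 with no upper limit, and the three-joint total runs to 15 (3 joints × 5, Protocol Appendix 1). A subject entering at 2 can improve by at most 2 points; one entering at 12 has far more room. Protocol 8.2 says that the CGIC rater "must have access to the TNmAS". Randomization is stratified by region only (SAP 5.2), so chance imbalance in baseline severity is handled by neither the design nor the CGIC model.

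At stake is power on one of two endpoints that must both reach 0.05 for 40 mg against placebo.

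**Working it through.** **Inputs from the documents.** 510 subjects, 170 per arm (Protocol Section 5; 3 × 170 = 510); two-sided 0.05 (Protocol 11.1); CGIC model terms as above.

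**Inputs assumed.** The text under the sample-size headings is absent from the public copy, so the planned power, effect size, SD and dropout are unknown and the sample size cannot be rebuilt. I take unadjusted CGIC power as 80% or 90%. R is the correlation of baseline TNmAS-MAL with Day 84 CGIC after the other model terms. The documents give no value, so the range starts at zero.

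**Step 1: effect implied by the starting power.** δ/SD = (z₀.₉₇₅ + z_power) × √(2/n).
- 80%: (1.960 + 0.842) × √(2/170) = 0.304
- 90%: (1.960 + 1.282) × √(2/170) = 0.352

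**Step 2: effect of the covariate.** The residual SD becomes SD × √(1 − R²), so power = Φ[(z₀.₉₇₅ + z_power)/√(1 − R²) − 1.960]. The equivalent number per arm is 170/(1 − R²). Example at R = 0.3 from 80%: 2.802/√0.91 = 2.937; 2.937 − 1.960 = 0.977; Φ(0.977) = 83.6%.

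| R | Variance removed | Power from 80% | Power from 90% | Equivalent n per arm |
|---|---|---|---|---|
| 0 | 0% | 80.0% | 90.0% | 170 |
| 0.1 | 1% | 80.4% | 90.3% | 172 |
| 0.2 | 4% | 81.6% | 91.1% | 177 |
| 0.3 | 9% | 83.6% | 92.5% | 187 |
| 0.4 | 16% | 86.4% | 94.3% | 202 |

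With 15% or 25% assumed dropout (144 or 127 per arm), and the effect re-scaled to the same starting power, the power figures do not change.

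**Step 3: cost.** One covariate uses one degree of freedom. It pays for itself above roughly R = √(1/(df − 1)). With df = 510 − 3 = 507 this is 0.044; with an assumed 60 center terms (df = 447) it is 0.047.

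**Step 4: check on a 7-point scale.** I simulated a single-visit CGIC, rounded and limited to −3 to +3, with no center effect and no dropout. Power without and with the covariate was 77.1% and 77.1% at R = 0, 77.7% and 78.2% at R = 0.1, and 80.2% and 83.3% at R = 0.3. Under the null, at R from 0 to 0.5, the unadjusted analysis rejected in 4.7–5.4% of runs and the adjusted one in 4.5–6.1% (2,000 runs each, Monte Carlo SE about 0.5 points). The unadjusted model holds its level. The highest adjusted figure, at R = 0.5, lies about two standard errors above 5%.

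**Step 5: is the covariate clean?** The tie rule chooses the analyzed limb partly from post-baseline scores. Limbs tied at baseline have the same baseline total, so the covariate takes the same value whichever limb is chosen. EDSS is less clear: Protocol 6.2 lists it after the first dose, while Protocol 7.4 puts Visit 2 clinical assessments before treatment assignment.

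**The case against.** The strongest reply is that nothing here is wrong. The protocol and SAP agree, randomization protects the comparison, study center is already in the model, and the covariate rule has been set. All of that stands. Several stronger readings are tempting, and the documents do not support them:

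- **That precision is known to be lost.** No correlation is given. At R = 0.1 or below the gain is negligible, and a range starting at 0.2 would leave out that case.
- **That the rater's access to the TNmAS ties baseline to CGIC as closely as to TNmAS-MAL change.** The change score subtracts baseline (SAP 7.4.1), so the two are coupled by construction. CGIC is rated directly as change. Access supports a link with TNmAS change more than with baseline level, and Appendix 3 tells the rater to look beyond spasticity.
- **That CGIC is the weaker co-primary.** Without the sample-size text, nothing shows which endpoint limits success.
- **That the missing-at-random assumption fails.** Baseline severity matters here only if it predicts both dropout and CGIC given the other terms, and no evidence of that is offered. The model uses Day 42 CGIC, early-termination visits include CGIC and are mapped to scheduled visits (SAP 7.3.3), and SAP 9.1.3 has mWOCF, penalty and pattern-mixture analyses.
- **That the must-win argument reaches PGIC.** PGIC is secondary and scheduled only at Visit 6.

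**Conclusion.** The point holds as a missed option for better precision. The CGIC model conditions on no baseline severity measure, the stated reason does not require that, and a suitable covariate is scheduled before treatment for every subject. The omission does not bias the treatment comparison or inflate type I error.

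Under the assumptions above, the power gain is nil at R = 0, 0.4 or 0.3 points at R = 0.1, and 6.4 or 4.3 points at R = 0.4 (from 80% or 90%). I am confident about the omission and about the low cost. I have no basis in the documents for saying that the gain would be material.

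**What to change.** Before unblinding:

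- In SAP 9.1.2, name Visit 2 TNmAS-MAL as a single fixed covariate in the CGIC MMRM.
- Carry the same term into the CGIC mWOCF ANCOVA and the pattern-mixture analysis (imputation and analysis models) in SAP 9.1.3 and, for consistency, into the PGIC model in SAP 9.2.2.
- Either align Protocol 11.4.1, which is an amendment needing sponsor and IRB/IEC approval (Protocol 12.2), or record the change in SAP 3.3, which now reports consistency with the protocol.
- Add EDSS only if the SAP names it definitively and its Visit 2 assessment is confirmed to precede the first dose. An optional covariate is not a prespecified one.

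The cost is about one degree of freedom and edits to a few SAP sections, with no new data. Timing matters: a covariate added after unblinding would be post hoc.
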